5.2.4.3. Toxicity Management Guidelines

When a patient experiences any Grade 3 or Grade 4 hematologic or non-hematologic toxicity, excluding infusion related reactions (Section 5.2.4.2) related to seribantumab, the following toxicity management guidelines should be followed:

Dose Interruptions and Reductions for Hematologic Toxicity

For \geq Grade 3 hematologic toxicity, seribantumab dosing will be held until resolving to \leq Grade 2 or the patient's baseline. Once the hematologic toxicity resolves to \leq Grade 2 or the patient's baseline, seribantumab will be restarted at a 25% reduction of the original dose.

For recurrence of a \geq Grade 3 hematologic toxicity, seribantumab will be held again until resolving to \leq Grade 2 or the patient's baseline. Once the hematologic toxicity resolves to \leq Grade 2 or the patient's baseline, seribantumab will be restarted at a 50% reduction of the original dose.

For patients who have had dose reductions of seribantumab due to hematologic toxicity, investigators may restart seribantumab at the original assigned dose, provided the toxicity has resolved to \leq Grade 1 on the reduced dose for at least one cycle of treatment. The Investigator should consult with the Medical Monitor and Sponsor prior to any planned dose re-escalation.

Seribantumab should be permanently discontinued if the patient experiences a recurrent Grade 3 or higher treatment related hematologic toxicity, despite a 50% dose reduction.

Dose Interruptions and Reductions for Non-Hematologic Toxicity

For \geq Grade 3 non-hematologic toxicity, seribantumab dosing will be held until resolving to \leq Grade 1 or the patient's baseline. Once the non-hematologic toxicity resolves to \leq Grade 1 or the patient's baseline, seribantumab will be restarted at a 25% reduction of the original dose.

For recurrence of a \geq Grade 3 non-hematologic toxicity, seribantumab will be held again until resolving to \leq Grade 1 or the patient's baseline. Once the non-hematologic toxicity resolves to \leq Grade 1 or the patient's baseline, seribantumab will be restarted at a 50% reduction of the original dose.

For patients who have had dose reductions of seribantumab due to non-hematologic toxicity, investigators may restart seribantumab at the original assigned dose, provided the toxicity has resolved to \leq Grade 1 on the reduced dose for at least one cycle of treatment. The Investigator should consult with the Medical Monitor and Sponsor prior to dose re-escalation.

Seribantumab should be permanently discontinued if the patient experiences a recurrent Grade 3 or higher treatment related non-hematologic toxicity, despite a 50% dose reduction.

Dose re-escalation is not permitted for patients who experience:

- Recurrent Grade 3 AEs determined to be clinically significant by the Investigator despite dose-reduction
- Recurrent Grade 4 AEs despite dose-reduction

Seribantumab should be permanently discontinued for patients who experience life-threatening Grade 4 AEs.

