5.2.5. Potential Toxicities with Seribantumab

Overall, seribantumab has been administered IV to 869 patients in ongoing and completed studies. In the CRESTONE study, as of 08May2021, diarrhea (8 patients, 53.3%), hypokalemia (5 patients, 33.3%), and fatigue (5 patients, 33.3%) were the most commonly reported TEAEs. Grade 3 TEAEs were experienced by 3 (20.0%) patients. A total of two SAEs have been reported in one patient. Both SAEs were Grade 2, resolved, and considered not related to seribantumab. Both events were associated with the patient's concurrent illness of non-serious AE of COVID-19 infections.

For additional information on the safety associated with seribantumab as a monotherapy and in combination with standard anticancer treatments, as well as for safety observations in Investigator sponsored single patient INDs, please refer to the current version of the Investigator's Brochure.

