5.3. Dose Modifications

Patients who experience a clinically significant AE (Grade \geq 3), may have seribantumab dosing held for up to 3 weeks to allow for recovery. Upon restarting treatment with study drug, the seribantumab dose will be reduced by either 25% (first occurrence) or 50% (recurrence) per Section 5.2.4.3, as follows:

Table 3: Dose Modification – Weekly Dosing

Original dose level	3,000 mg
25% dose reduction	2,250 mg
50% dose reduction	1,500 mg

For patients who meet criteria to transition to Q2W dosing, please discuss with and obtain approval from the Sponsor before reducing the dose. Patients who experience clinically significant AEs

related to seribantumab during Q2W dosing must have seribantumab withheld until the AE resolves according to Section 5.2.4.3.

Seribantumab should be permanently discontinued for patients who experience life-threatening grade 4 AEs. Seribantumab should also be permanently discontinued for patients who experience clinically significant, drug-related AEs requiring a recovery period of longer than 3 weeks, unless there is compelling, objective radiological evidence of response and no alternative treatment. The Sponsor and Investigator must agree that continuation of seribantumab is in the best interest of the patient, and the patient agrees.

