Given that the *NRG1* fusion patients to be enrolled in the CRESTONE study are expected to be heavily pretreated, metastatic patients who have exhausted standard treatment options, the initial dosing regimen was designed to deliver rapid steady state levels with a 4-week induction phase consisting of once weekly dosing. This induction treatment course was to be followed by a consolidation (3,000mg IV Q2W x 6 doses) and maintenance (3,000 mg IV Q3W) phase of dosing, in the initially approved Protocol Version 2.0. These subsequent dosing phases were expected to be well tolerated, and they were based on previously defined thresholds (e.g., > 100 mg/L minimum and ≥ 500 mg/L average serum concentrations), which were established in non-*NRG1* fusion positive cancer models and patients, which may not be relevant to tumors harboring oncogenic *NRG1* gene fusions.

Further PK modeling (Data on file, Feb 2020; [NCR001-01 PK Report](#)) was performed prior to the initiation of the CRESTONE study to support the initial planned weekly induction dosing regimens (e.g., Induction Regimen 1: 3,000 mg IV week 1 followed by 2,000 mg IV weeks 2, 3 and 4; and Induction Regimen 2: 3,000 mg IV once weekly x 4 doses). The results from this initial PK modeling (Data on file, Feb 2020; [NCR001-01 PK Report](#)) indicated the range of predicted C_{max} and C_{avg} values with Induction Regimen 1 would be comparable to levels observed in patients treated with the 40/20 mg/kg weekly dosing regimen from the initial monotherapy study ([MM-121-01-100](#) study), while Induction Regimen 2 would increase exposure during the initial 4 weeks by approximately 60% compared to the previously studied 40/20 weekly regimen.

Prior Induction Regimens

Induction Regimen 1: Seribantumab 3,000 mg 1-h IV as a loading dose at the C1W1 visit, followed by 2,000 mg 1-h IV once weekly at C1W2, C1W3 and C1W4. There were no DLTs observed with Induction Regimen 1. Upon review and recommendation by the SRC, the next 6 patients enrolled and initiated treatment with Induction Regimen 2.

Induction Regimen 2: Seribantumab 3,000 mg 1-h IV once weekly at the C1W1, C1W2, C1W3 and C1W4 visits. There were no DLTs observed in the first 6 patients treated with Induction Regimen 2. Upon review and recommendation by the SRC, all subsequently enrolled patients treated under Protocol Version 2.0 initiated treatment with Induction Regimen 2.

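### Sections 5.2.4.3 and 5.3 do not say whether Grade 3 or higher events are counted within or across toxicity classes; read literally, a patient on 1,500 mg restarts at 2,250 mg after a first severe toxicity of the other class

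*Protocol*

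**What the plan says.** Protocol 5.2.4.3 treats hematologic and non-hematologic toxicity separately. In each class a first Grade 3 or higher event leads to a hold, after which "seribantumab will be restarted at a 25% reduction of the original dose". A recurrence in the same class leads to a restart at half the original dose. Table 3 in 5.3 gives the levels as 3,000, 2,250 and 1,500 mg.

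Four other rules bear on the restart dose:

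- **Re-escalation (5.2.4.3).** After a reduction, "investigators may restart seribantumab at the original assigned dose" once the toxicity has been at Grade 1 or lower for at least one cycle on the reduced dose. The investigator is expected to consult the Medical Monitor and the Sponsor beforehand.
- **Ban (5.2.4.3).** "Dose re-escalation is not permitted for patients who experience" either "Recurrent Grade 3 AEs determined to be clinically significant by the Investigator despite dose-reduction" or recurrent Grade 4 events despite reduction.
- **Stop rule (5.2.4.3).** "Seribantumab should be permanently discontinued if the patient experiences a recurrent Grade 3 or higher treatment related non-hematologic toxicity, despite a 50% dose reduction". A parallel sentence covers hematologic toxicity. Life-threatening Grade 4 events end treatment regardless.
- **Section 5.3.** On restart after a Grade 3 or higher event, "the seribantumab dose will be reduced by either 25% (first occurrence) or 50% (recurrence) per Section 5.2.4.3". No toxicity class is named.

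No sentence addresses a patient who has already been reduced for the other class.

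**The concern.** Each ladder counts its own events and measures its steps from 3,000 mg rather than from the current dose. The first step of the second ladder therefore points to 2,250 mg even when the patient is already at or below that level. Sites could differ on whether to hold or step down from 2,250 mg. A site following the ladder literally could raise the dose from 1,500 mg straight after a new severe toxicity. The stake is patient safety in a small number of patients, not the efficacy analysis.

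**Working it through.** **Inputs.** Original dose 3,000 mg weekly (Protocol 5.2.3.1); 25% and 50% reductions of the original dose (5.2.4.3); dose levels in Table 3 (5.3); 28-day cycle, so four weekly doses.

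**Step 1: reproduce Table 3.** 3,000 × (1 − 0.25) = 2,250 mg and 3,000 × (1 − 0.50) = 1,500 mg. Both match.

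**Step 2: apply the ladders as written.** Keep a separate event count per class. H is a hematologic and N a non-hematologic event of Grade 3 or higher.

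| Sequence | Dose path (mg) | Last step |
|---|---|---|
| H, N | 3,000 → 2,250 → 2,250 | no change |
| H, N, N | 3,000 → 2,250 → 2,250 → 1,500 | reduction |
| H, H, N | 3,000 → 2,250 → 1,500 → 2,250 | increase |

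Swapping the classes gives the same result. The 2,250 mg restart arises only for the first event in the other class; a recurrence there gives 1,500 mg.

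**Step 3: Case A, patient on 2,250 mg.** Counting within class: 2,250 / 2,250 = 1.00, no reduction. Counting across classes, the second event is a recurrence: 1,500 / 2,250 = 0.667, a 33% reduction. Over four doses this is 4 × 2,250 = 9,000 mg against 4 × 1,500 = 6,000 mg.

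**Step 4: Case B, patient on 1,500 mg.** 2,250 − 1,500 = 750 mg; 2,250 / 1,500 = 1.50, an increase of 50%, or 6,000 to 9,000 mg per cycle.

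**Step 5: test Case B against the other rules.**

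- *Section 5.3* says the dose goes down on restart. An increase is at odds with that, although 5.3 refers back to 5.2.4.3 for the detail.
- *Permitted re-escalation* is a return to the original dose after a recovery period. A move to 2,250 mg at restart is not that.
- *The ban* is written for re-escalation, so using it here is an inference. If it is used, its reach depends on how the patient came to 1,500 mg. Suppose the second same-class event occurred on 2,250 mg. The ban then applies if that event was Grade 4, or Grade 3 judged clinically significant. Suppose instead that the patient had been returned to 3,000 mg before the second event. That event was not on a reduced dose, so the ban bites only if the third event, on 1,500 mg, counts as recurrent across classes. The text does not say whether it does.
- *The consultation* is also tied to re-escalation. A site that sees itself as taking the ladder's first step may not think it applies.
- *The stop rule* at the 50% dose requires a recurrence in a named class, so a first event of the other class is not clearly covered.

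**Step 6: how often.** Case A needs two, and Case B three, Grade 3 or higher events across both classes. Section 5.2.5 reports that "Grade 3 TEAEs were experienced by 3 (20.0%) patients". That is 3 of 15, with an exact (Clopper-Pearson) 95% interval of 4.3% to 48.1%, all causes and classes together. Appendix A adds that "There were no DLTs observed in the first 6 patients treated with Induction Regimen 2". For 0 of 6 the upper exact limit is 1 − 0.025^(1/6) = 0.459, about 46%. The observation window for DLTs is 28 days, so it says little about repeated events. No count of repeated or cross-class events is given.

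**The case against.** The best defense is that Case B is a strained reading. The ladders stand under headings about interruptions and reductions, 5.3 speaks of a reduced dose, and the only written increase requires at least one cycle at Grade 1 or lower. The ban refers to adverse events without naming a class, and 5.3 appears to treat Grade 3 or higher as clinically significant, which would narrow the gaps in the ban. The Medical Monitor and the Sponsor are to be consulted before any re-escalation. The sponsor also ended the study before full enrollment (SAP Section 8), so few patients, if any, may still be dosed.

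Much of this stands. Most investigators would probably not raise the dose. But the ban and the consultation help only if the restart counts as a re-escalation, and the section describes that only as a return to the original dose. The literal first step still points to 2,250 mg.

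For Case A the defense succeeds further. A reader might infer that holding at 2,250 mg contradicts 5.3. It does not clearly do so: 5.3 defers to 5.2.4.3, Table 3 measures reductions from 3,000 mg, and 2,250 mg is its first-occurrence level. Holding the dose after a first toxicity of a different kind is also a defensible choice.

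**Conclusion.** The point holds as a minor dosing-text problem. Case B is the substantive part: a stated rule, applied literally, gives a restart 750 mg (50%) above the held dose after a new severe toxicity, and no other sentence clearly prevents it. Case A is an ambiguity between 2,250 and 1,500 mg. Both conclusions assume that events are counted within class, as 5.2.4.3 is written.

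Three further inferences are not supported. First, the plan does not leave the restart dose blank: the ladder yields 2,250 mg, and what is missing is a rule for a patient already reduced for the other class. Second, one cannot say that the ban usually blocks the increase. That rests on an assumed route to 1,500 mg and on extending the ban to a restart at 2,250 mg, and the documents give no frequency. Third, the absence of DLTs in all 12 run-in patients should not be pooled as reassurance about 3,000 mg weekly, because six of them received 2,000 mg in weeks 2 to 4 (Appendix A).

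The need for two or three severe events across both classes suggests that such cases are rare, but the number affected cannot be estimated. ORR and sample size are not affected.

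**What to change.** Add to 5.2.4.3 and 5.3: *After any Grade 3 or higher toxicity of either class, the restart dose must never exceed the dose being given at onset; any later increase may occur only under the re-escalation conditions in Section 5.2.4.3.* This closes Case B however events are counted.

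As a secondary clarification, the same letter can state whether occurrences are pooled across classes, which settles Case A. If they are pooled, it should also say whether a patient on 1,500 mg restarts at that dose or stops, since Table 3 has no lower level.

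The cost is a short clarification letter, needed only if a patient is still on treatment, which the documents do not show. No new data or procedures are required. The by-patient administration listing already planned in SAP 6.4.1 should let a reader see whether any restart exceeded the held dose.

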5.2.5. Potential Toxicities with Seribantumab

Overall, seribantumab has been administered IV to 869 patients in ongoing and completed studies. In the CRESTONE study, as of 08May2021, diarrhea (8 patients, 53.3%), hypokalemia (5 patients, 33.3%), and fatigue (5 patients, 33.3%) were the most commonly reported TEAEs. Grade 3 TEAEs were experienced by 3 (20.0%) patients. A total of two SAEs have been reported in one patient. Both SAEs were Grade 2, resolved, and considered not related to seribantumab. Both events were associated with the patient's concurrent illness of non-serious AE of COVID-19 infections.

For additional information on the safety associated with seribantumab as a monotherapy and in combination with standard anticancer treatments, as well as for safety observations in Investigator sponsored single patient INDs, please refer to the current version of the Investigator's Brochure.

5.3. Dose Modifications

Patients who experience a clinically significant AE (Grade \geq 3), may have seribantumab dosing held for up to 3 weeks to allow for recovery. Upon restarting treatment with study drug, the seribantumab dose will be reduced by either 25% (first occurrence) or 50% (recurrence) per Section 5.2.4.3, as follows:

Table 3: Dose Modification – Weekly Dosing

Original dose level	3,000 mg
25% dose reduction	2,250 mg
50% dose reduction	1,500 mg

For patients who meet criteria to transition to Q2W dosing, please discuss with and obtain approval from the Sponsor before reducing the dose. Patients who experience clinically significant AEs

related to seribantumab during Q2W dosing must have seribantumab withheld until the AE resolves according to Section 5.2.4.3.

Seribantumab should be permanently discontinued for patients who experience life-threatening grade 4 AEs. Seribantumab should also be permanently discontinued for patients who experience clinically significant, drug-related AEs requiring a recovery period of longer than 3 weeks, unless there is compelling, objective radiological evidence of response and no alternative treatment. The Sponsor and Investigator must agree that continuation of seribantumab is in the best interest of the patient, and the patient agrees.

5.4. Study Treatment Discontinuation

A patient may withdraw from the study at any time and for any reason. Over the course of the study, the Investigator and/or Sponsor should withdraw a patient from treatment for any of the following reasons:

- Disease progression (as assessed using RECIST v1.1). Note: Patients with disease progression per RECIST v1.1 who, in both the Investigator's and Sponsor's opinions, may continue to derive clinical benefit, and who meet the criteria listed in Section 5.4.1, may be allowed to continue treatment with written approval from the Sponsor.
- Clinically significant drug-related toxicity requiring a recovery period of longer than 3 weeks, unless there is compelling, objective radiological evidence of response, no alternative treatment, and the Sponsor and Investigator agree that continuation of seribantumab is in the best interest of the patient, and the patient agrees
- Intercurrent illness compromising the ability to fulfill protocol requirements
- Requirement for alternative treatment in the opinion of the Investigator
- Significant non-compliance to protocol
- Withdrawal of consent by the patient
- Patient is lost to follow-up
- Death

When a patient is discontinued from treatment for any reason, they are to undergo the assessments in the End of Treatment visit within 4 weeks of the last dose and prior to initiating any subsequent anti-cancer therapy. All patients who discontinue treatment as a result of an adverse event (AE) must be followed until resolution or stabilization of the AE. At the time a patient withdraws from study treatment, an attempt should be made to determine the reason(s) for discontinuation.

Upon withdrawal from treatment, the patient will continue to be followed for survival and subsequent disease and treatment information every 3 months after completion of the End of Treatment visit. If a patient does not return to the clinic for the end of treatment visit or is not reached for overall survival follow-up, at least 3 documented attempts, including one via certified mail, should be made to contact the patient. If the patient does not respond to these requests, the date of death should be captured from public records.

5.4.1. Study Treatment Beyond Progression

As noted in Section 5.4, patients with disease progression per RECIST v1.1 who, in the Investigator's and Sponsor's opinions, may continue to derive clinical benefit, may be eligible to continue in the study if they meet the criteria outlined below:

- absence of clinical symptoms or signs indicating clinically significant disease progression;
- no decline in the ECOG performance status;
- absence of rapid disease progression or threat to vital organs or critical anatomical sites (e.g., central nervous system metastasis, respiratory failure due to tumor compression, spinal cord compression) requiring urgent alternative medical intervention;
- no significant, unacceptable, or irreversible toxicities related to the trial treatment;
- have written approval of the Sponsor;
- have signed an ICF agreeing to continue treatment; and
- no other treatment discontinuation criteria are met.

Patients must permanently discontinue seribantumab treatment if subsequent imaging demonstrates further disease progression of $\geq 10\%$ in the target lesions, unequivocal or further progression in non-target lesions, and/or the appearance of new lesions.

5.5. Concomitant and Prohibited Therapies

Standard supportive medications may be used in accordance with institutional guidelines and Investigator discretion. These may include hematopoietic growth factors to treat neutropenia, thrombocytopenia or anemia in accordance with American Society of Clinical Oncology (ASCO) Guidelines (but not for prophylaxis in Cycle 1), transfusions, anti-emetics, anti-diarrheals, antibiotics, antipyretics, and corticosteroids (up to 10 mg per day prednisone or equivalent, unless a compelling clinical rationale for a higher dose is articulated by the Investigator and approved by the Sponsor; permitted corticosteroid uses include topical/cutaneous, ophthalmic, nasal and inhalational steroids, as well as short courses to treat asthma, chronic obstructive pulmonary disease, or other non-cancer related conditions).

All concomitant medications, including transfusions of blood products, will be recorded on the appropriate page of the case report form. Concomitant therapy (non-investigational products) includes any prescription medication, over-the-counter preparation, herbal therapy, or radiotherapy used by a patient between the 28 days preceding study treatment initiation and the study treatment discontinuation visit. After the End of Treatment Visit, only anti-cancer therapies will be collected in addition to survival information.

The following therapies are not permitted while on study treatment:

- Other anti-neoplastic therapy, including cytotoxics, targeted agents, endocrine therapy, or other antibodies (patients who have been on gonadotropin-releasing hormone analogues for more than 90 days prior to study entry may continue while on study)

- Any other investigational therapy

5.5.1. Concurrent Palliative Radiotherapy and Elective Procedures

Palliative radiotherapy to specific sites of disease is permitted if considered medically necessary by the treating physician. Seribantumab treatment should be interrupted during palliative radiotherapy, stopping 3 days before and resuming treatment no earlier than 1 day thereafter. In general, target lesions being used to measure response should not be irradiated without discussion with the Sponsor and may be reason for the patient to be removed from study for progressive disease. Irradiated lesions will be considered not evaluable for response but can still be used to assess disease progression. The intensities, number, and dates of doses received for allowed palliative radiotherapy should be recorded on the appropriate eCRF.

Although seribantumab is not expected to significantly affect wound healing, any unusual findings should be recorded as potential AEs. In the event elective procedures, including surgery, are necessary during study participation, seribantumab dosing should be stopped 3 days before surgery and resumed no sooner than 24 hours after surgery.

